## 9.3 Study Endpoints

### 9.3.1 Primary Endpoint

#### Grade 2 Adverse Events

The safety/toxicity endpoint is clinical or laboratory evidence of a Grade 2 or higher Adverse Event as defined by the DAIDS Table for Grading Adult and Pediatric Adverse Events, Version 2.1, July 2017 and the Female Genital Grading Table for Use in Microbicide Studies (Appendix 1 to the DAIDS Table for Grading Adult and Pediatric Adverse Events, (Dated November 2007).

### 9.3.2 Secondary and Exploratory Endpoints

The secondary and exploratory endpoints of this study are as follows:

#### Secondary: Acceptability

Reports of overall acceptability of the film and qualities of the experience with the film will be measured using a self-report survey drawing items from two sources. Overall acceptability is measured using standard language in market research methodology, each using a 5-point agreement scale followed by an open-ended explanation. Assessment of film-specific qualities of the experience is assessed by a 9-item scale drawn from previous research with participant-inserted films. Questions assess perceptions of leaking, vaginal dryness, and sensation of the film inside the vagina during and after insertion.

#### Exploratory: Vaginal Microenvironment

Given that there is no non-product use arm, participants will serve as their own control. Assessment of baseline microenvironment will take place during the enrollment visit with the exception of CVL properties. CVL will be obtained at the screening visit so that the microenvironment can recover prior to study product administration at the enrollment visit.

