## **4.6 Expected Duration of Participation**

The duration of study participation per woman is expected to be approximately 5-11 weeks. This includes the screening period.

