## **5.4 Inclusion Criteria**

Women must meet all the following criteria to be eligible for inclusion in the study:

- 1) Age 18 through 45 years (inclusive) at screening
- 2) Able and willing to provide written informed consent to be screened for and to take part in the study.

- 3) Able and willing to provide adequate locator information
- 4) HIV-uninfected based on testing performed by study staff at screening (per algorithm in Appendix II)
- 5) In general good health as determined by the site clinician
- 6) Agree to be sexually abstinent for 48 hours prior to each visit and from Visit 2 to seven days after Visit 3
- 7) At screening, agrees to abstain from any other intravaginal product or penetration (including sex toys, excluding tampons) for 48 hours prior to each visit and between Visit 2 and 3.
- 8) Willingness to undergo all study-related assessments and follow all study-related procedures
- 9) At screening and enrollment, agrees not to participate in other research studies involving drugs, medical devices, or vaginal products while enrolled in this trial

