## **5.5 Exclusion Criteria**

Women who meet any of the following criteria by participant report will be excluded from the study. Of note, the study is limited to premenopausal women with an intact uterus because the mucosal immune environment differs substantially between pre- and post- menopausal women. Therefore, inclusion of post-menopausal women would introduce heterogeneity into the population.

- 1.) Menopause (as defined as amenorrhea for one year or more without an alternative etiology)
- 2.) Hysterectomy
- 3.) Participant report of any of the following:
  - a) Known adverse reaction to any of the study products (ever)
  - b) Known adverse reaction to latex (ever)
  - c) Non- therapeutic injection drug use in the 12 months prior to Screening
  - d) Surgical procedure involving the pelvis in the 90 days prior to enrollment (includes dilation and curettage or evacuation, and cryosurgery; does not include cervical biopsy for evaluation of an abnormal pap smear)
  - e) Participation in a drug, spermicide and/or microbicide study in the 30 days prior to enrollment or anticipated participation in an investigational drug study until completion of the study
  - f) Currently pregnant or pregnancy within 42 days prior to enrollment
  - g) Currently lactating
  - h) Use of a diaphragm, NuvaRing®, or spermicide for contraception
  - i) Internal vaginal use of any device or product (except tampons) in the 48 hours prior to enrollment
- 4.) Urogenital infection or suspected infection within 14 days of enrollment including: symptomatic candidiasis, trichomonas vaginalis, and symptomatic bacterial vaginosis; or cervical infection, including *N. gonorrhoeae* (GC), *C. trachomatis* (CT), or mucopurulent cervicitis; syphilis; HSV lesions, or other sores (Note: seropositive HSV without active lesions will not be excluded); acute pelvic inflammatory disease; urinary tract infection; recent exposure to a partner with GC, CT, Trichomonas, syphilis, or NGU

- 5.) Antibiotic or antifungal therapy (vaginal or systemic) within 14 days of enrollment
- 6.) As determined by the PI, has any significant uncontrolled active or chronic cardiovascular, renal, liver, hematologic, neurologic, gastrointestinal, psychiatric, endocrine, respiratory, immunologic disorder or infectious disease
- 7.) Menses-like bleeding at the time of the Enrollment visit\* or expected menses-like bleeding within 14 days of the Enrollment visit  

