## **7.2 Visit 1: Screening Visit**

Screening may take place up to 45 days prior to Enrollment. Screening procedures may occur over several visits. A combined written informed consent for screening and enrollment will be obtained before any screening procedures are initiated. For participants who do not meet the eligibility criteria, screening will be discontinued once ineligibility is determined.

The table below outlines procedure to take place at the Screening Visit.

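### The only baseline lavage (CVL) is taken at screening, but the exclusions that would keep it clean are dated from Enrollment, so the exploratory within-arm pre/post CVL comparisons can include recovery from a disturbed baseline

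*Combined protocol and SAP*

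**What the plan says.** All places are in the combined protocol and SAP.

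- **Design (9.3.2, Vaginal Microenvironment).** "Given that there is no non-product use arm, participants will serve as their own control". Baseline for Nugent score, culture and qPCR comes from Enrollment. CVL is the exception: "CVL will be obtained at the screening visit so that the microenvironment can recover prior to study product administration at the enrollment visit".
- **Timing (7.2).** "Screening may take place up to 45 days prior to Enrollment. Screening procedures may occur over several visits". Table 2 lists CVL at Visit 1. Table 3 and the Appendix 1 schedule list none at Visit 2, so Visit 1 supplies the only pre-film CVL. Post-film CVL is taken at Visits 3 and 4.
- **Exclusions (5.5).** Item 4 reads "Urogenital infection or suspected infection within 14 days of enrollment including" and goes on to a list of conditions. Item 5 applies the same 14 days before Enrollment to antibiotic or antifungal therapy. Item 7 concerns menses-like bleeding at Enrollment or expected in the 14 days after it. Item 3i reads "Internal vaginal use of any device or product (except tampons) in the 48 hours prior to enrollment". All four are dated from Enrollment, and the rescheduling rule for bleeding in 7.3 also covers Enrollment only.
- **Inclusion (5.4).** Item 6 asks for 48 hours of sexual abstinence before each visit. Item 7 adds 48 hours without products or penetration, worded "At screening, agrees to abstain from any other intravaginal product or penetration".
- **Analysis (9.6.3).** CVL changes are tested within each arm by paired t and Wilcoxon signed-rank tests and between arms by ANOVA and Kruskal-Wallis. Time since last menstrual period is named as a potential confounder.

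**The concern.** In an own-control design the pre-film sample does the work of a control group. Here the conditions for a clean sample protect Visit 2, while the CVL that serves as baseline is taken earlier. A woman lavaged at Visit 1 while bleeding, or with an infection that is then treated, can satisfy every written criterion by Enrollment and keep that CVL as her pre value.

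The protocol itself treats these conditions as relevant to the endpoints. Section 9.1 gives ruling out other causes of inflammation as the purpose of screening tests, and 9.3.2 says that microbial flora may alter mucins. At stake is whether a within-arm change in cytokines, mucins, glycome or antiviral activity can be attributed to the film. A baseline compromised at collection cannot be recovered later.

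**Working it through.** The plan states no figure on this point. Section 9.2 sizes the study for adverse events and contributes only the arm size (16).

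**1. Dates side by side**

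| Condition | Look-back from Enrollment | Rule on the day of the baseline CVL |
|---|---|---|
| Urogenital infection | 14 days (5.5 item 4) | none |
| Antibiotic/antifungal | 14 days (5.5 item 5) | none |
| Menses-like bleeding | at Enrollment or expected within 14 days after (5.5 item 7) | none |
| Vaginal product | 48 hours (5.5 item 3i) | 48 hours before each visit, agreed at screening (5.4 item 7) |
| Sex | none in 5.5 | 48 hours before each visit (5.4 item 6) |

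**2. Window arithmetic**

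The maximum gap is 45 days: "Screening may take place up to 45 days prior to Enrollment". A CVL on days -45 to -15 precedes both 14-day look-backs: 45 - 14 = 31 of 45 permitted days (31/45 = 69%). This counts permitted days and is not a probability. For an infection that needs treatment the room is smaller, because treatment must also end before the look-back begins.

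Such gaps look ordinary. Section 4.6 says "The duration of study participation per woman is expected to be approximately 5-11 weeks". Five weeks less 21 days of follow-up is 35 - 21 = 14 days. With the Visit 4 window of 18-25 days, it is 35 - 25 = 10 to 35 - 18 = 17 days. Even the shortest expected participation puts Visit 1 near the start of the look-back.

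**3. What would be known at Visit 1**

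GC/CT and Trichomonas NAAT are collected at the same visit as the CVL, so results can follow the lavage. Wet mount is only as indicated and no Gram stain is done, so BV status on the CVL day may go unrecorded.

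**4. Illustrative size**

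Assumptions, none from the documents: a fraction f of baselines is shifted by 1 SD; pre/post correlation is 0.5; the film has no true effect.

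- Bias in mean change = f × 1 SD, in the direction opposite to the baseline shift. For f = 0.10 to 0.30 this is 0.10 to 0.30 SD.
- Standard error in one arm = sqrt(2 × (1 - 0.5) / 16) = 0.25 SD.
- Ratio: 0.10/0.25 = 0.4 and 0.30/0.25 = 1.2 standard errors. This standard error leaves out the extra spread that a mixture of shifted and unshifted baselines adds.
- Simulation of the paired t-test at nominal 5%, n = 16, with that spread included: rejection in 6.5% (f = 0.10), 10.3% (f = 0.20) and 16.8% (f = 0.30) of arms.

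**5. Direction**

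The post-film samples are not uniformly clean either. Visit 4 (days 18-25) has no bleeding rule and lies beyond the 14 days in which no menses is expected, so bleeding can fall on the post sample and push the change the other way. The documents do not say how infection, treatment or bleeding moves any CVL marker.

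**The case against.** The strongest reply is that the early CVL is deliberate and that the plan has protections. Lavage disturbs the environment, so taking it before Enrollment is sound; nothing here argues against that. Screening tests exist to rule out other causes of inflammation (9.1), about 150 women are screened to find 64 with normal reproductive tracts (9.2), screening stops once a woman is ineligible (7.2), and exclusion 8 lets the investigator exclude conditions that would complicate interpretation. Time since last menstrual period is a planned confounder.

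These points show intent and discretion, but no requirement. An infection that resolved more than 14 days before Enrollment is not ineligibility as written. Paired t and Wilcoxon tests take no covariate, and menstrual timing does not address infection or treatment.

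Several stronger readings are tempting and should not be made:

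- *That the bias always makes the film look harmless.* The bleeding gap at Visit 4 can work the other way, and antiviral, lectin and mucin measures need not move as cytokines do.
- *That the bias reaches 0.8-2.4 standard errors.* That takes all 64 women as one paired sample (standard error 0.125 SD). Section 9.6.3 specifies paired tests within each arm of 16.
- *That sex and product exposure before Visit 1 is uncontrolled.* Inclusion items 6-7 cover the 48 hours before each visit, and pre-screening or multi-visit screening can convey this in time. Item 7 is agreed at screening and pre-screening is optional, so a gap remains, but this is the weakest part of the point.
- *That a CVL may be repeated only for laboratory problems.* Section 7.7 allows procedures to be repeated as clinically indicated and for other reasons. It does not require it.

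**Conclusion.** The point holds within limits. From the text alone, the only pre-film CVL is taken at Visit 1, the four exclusions are dated from Enrollment, and nothing requires a disturbed Visit 1 CVL to be deferred or left out. The within-arm paired CVL comparisons can therefore mix film effect with recovery.

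Size and direction are not determinable from the documents. The 0.10-0.30 SD (0.4-1.2 standard errors in an arm of 16) rests wholly on the assumed 10-30% fraction, 1 SD shift and 0.5 correlation.

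The reach is narrow. Only exploratory CVL endpoints are touched. Between-arm comparisons of change are largely protected, because randomization should spread disturbed baselines across arms, at some loss of precision. The primary safety endpoint, acceptability, and the Nugent, culture and qPCR baselines from Visit 2 are unaffected. It is worth correcting because the remedy is cheap and the sample cannot be retaken once the film is in place.

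**What to change.** 1. **Collection (7.2 and Table 2).** Collect the baseline CVL only when the sampling conditions already used for Enrollment hold on the CVL day: no menses-like bleeding, no known or suspected urogenital infection and no antibiotic or antifungal use in the previous 14 days, and 48 hours without sex or vaginal products. Otherwise defer it to a later screening visit, which 7.2 already permits, early enough before Enrollment to keep the recovery purpose in 9.3.2. The protocol team should state that interval. A routine second lavage is not proposed, since one close to Enrollment could defeat that purpose.
2. **Recording.** On the CVL day, record infection status (adding Visit 1 NAAT results when they return), treatment, bleeding, and sex or product exposure.
3. **Analysis (9.6.3).** Add a sensitivity analysis that repeats the paired CVL comparisons without baselines found to be affected, including those identified only by a later NAAT result.

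The cost is protocol wording, a few data fields, an extra screening visit for women who do not meet the conditions, and slightly fewer pairs in the sensitivity analysis.

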#### *Levels of lectin binding and mucins measured in CVL samples*

Endogenous and exogenous glycolytic enzymes, formulated microbicide products, and microbial flora interact with mucins and may alter their structure and function. These alterations may be detected with lectins, which are sugar specific binding molecules, and can be bound to reporter molecules (such as horseradish peroxidase) in an ELISA type assay.

#### *Changes in the Glycome*

Lectin microarray will be used to assess changes in the glycome.

#### *Nugent Score*

Clinically significant changes in vaginal flora will be evaluated by a change in the Nugent score baseline (Visit 2, pre-exposure) to Visit 5. The Nugent score is graded 1 to 10 as follows:

Normal, 0 to 3

Intermediate, 4 to 6

BV, 7-10

Any shift from normal at baseline to intermediate or BV at Visit 3 or 4, or shift from intermediate or BV to normal at Visit 3 or 4 will be considered a scientifically meaningful change in vaginal microbiota.

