### **3.3 Exploratory Objectives**

- **Vaginal Microenvironment**

- To compare the effects of the placebo film on the vaginal microbiota and glycome pre and post study product use.

- **Persistence**

- To describe the persistence of the placebo vaginal film at 3, 7, 10 and 14 days after insertion

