### **9.6.3 Secondary and Exploratory Endpoint Analysis**

Summary statistics of frequencies, percentages, and 95% confidence intervals will be provided for categorical data. Means, standard deviations, medians, ranges and 95% confidence

intervals will be provided for continuous data. Methods for the analyses of the secondary endpoints are described below.

One-way analysis of variance (ANOVA) and Kruskal-Wallis tests will be used, where appropriate, to evaluate differences in the following continuous variables between the study arms: levels of glycoproteins and mucins in CVL, levels of cytokines and innate immunity factors, and antiviral activity in CVL. Between groups, pre- to post-exposure changes in the above endpoints will also be evaluated using ANOVA and Kruskal-Wallis tests, where appropriate, while paired Student's t- and Wilcoxon signed-rank tests will be used to evaluate these changes within each study arm. Mixed effects linear regression will be used to evaluate associations between days of exposure to study product and these outcomes.

Nugent score will be categorized as follows: normal (score 0-3), intermediate (score 4-6), and bacterial vaginosis (score 7-10). Differences in the categorized Nugent score pre and post exposure levels will be evaluated using Fisher's exact, while McNemar's tests will be used to evaluate pre- to post-exposure shifts between normal (score 0-3) and abnormal (score 4-10) vaginal microflora within each study arm.

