Prevalence of microorganisms at each visit will be compared between the study arms using Fisher's exact tests, while pre- to post-exposure shifts will be evaluated within each group using McNemar's tests. Differences between the study arms in the quantity of microorganisms at each visit, as well as the change in quantity, will be evaluated using Mann-Whitney U tests. Meaningful changes will be defined by greater than or equal to 1 log changes in dominant members of the microflora, including Lactobacillus (H2O2 positive and negative strains), anaerobic gram negative rods, Gardnerella vaginalis, Candida species, facultative gram negative rods, Streptococci and facultative gram positive cocci and rods. Fisher's exact tests will be used to evaluate differences in these changes between study arms. Mixed effects linear regression (for continuous outcomes) and generalized estimating equations (for binary outcomes) will be used to evaluate associations between days of exposure to study product and these outcomes.

Time since last menstrual period will be included as a potential confounder in these analyses.

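### The exploratory Nugent change rule pools worsening with improvement, and no planned Nugent readout counts women who move from intermediate flora to BV (minor, free to fix)

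*Combined protocol and SAP*

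**What the plan says.** The exploratory objective in Section 3.3 is "To compare the effects of the placebo film on the vaginal microbiota and glycome pre and post study product use". Section 9.3.2 explains the comparison: "Given that there is no non-product use arm, participants will serve as their own control".

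Under Nugent Score, Section 9.3.2 sets three bands: normal 0 to 3, intermediate 4 to 6, BV 7 to 10. It says that flora will be "evaluated by a change in the Nugent score baseline (Visit 2, pre-exposure) to Visit 5". It then gives the event, judged at either follow-up visit: "Any shift from normal at baseline to intermediate or BV at Visit 3 or 4, or shift from intermediate or BV to normal". Any such move, in either direction, carries one label: it "will be considered a scientifically meaningful change in vaginal microbiota".

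Section 9.6.3 plans two tests on the categories. One sentence begins "Differences in the categorized Nugent score pre and post exposure levels will be evaluated using" and names Fisher's exact test. The other applies McNemar's test to pre- to post-exposure "shifts between normal (score 0-3) and abnormal (score 4-10) vaginal microflora within each study arm". Table 7 summarises the Nugent change as a count, a percentage and a 95% interval, and names no direction.

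Three other places bear on the point. Section 5.5 lists BV as an exclusion only when symptomatic. Section 8.3 excepts asymptomatic BV from the adverse event definition. The schedule in Appendix 1 has Gram stains at Visits 2, 3 and 4 and no visit after Visit 4.

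**The concern.** With no arm without product, the informative flora readout is each woman's own move from baseline, and its direction matters. The rule gives the same label to a woman who goes from normal to BV and to one who goes from BV to normal. It gives none to a woman who goes from intermediate to BV. A woman who starts intermediate can therefore be flagged only if she improves.

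Such women can enrol, because the flora-related exclusion is symptomatic BV. If their move to BV causes no symptoms, it is not an adverse event either. At stake is how clearly an exploratory result can be read: the planned percentage does not tell the reader how many women's flora got worse.

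**Working it through.** **Inputs.** Categories and event rule: Section 9.3.2. Tests: Section 9.6.3. Summary: Table 7. Sample size: 64 women, 16 per arm, Section 9.2. The plan gives no expected rate, power or margin for the Nugent rule, so it has no figure of its own to reproduce.

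**Step 1, list the moves.** Write N, I and B for normal, intermediate and BV. NI means normal at baseline and intermediate at follow-up, and so on.

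| Move | Direction | Counted by the rule | In the McNemar test (0-3 v 4-10) |
|---|---|---|---|
| NI | worse | yes | discordant, worse |
| NB | worse | yes | discordant, worse |
| IB | worse | no | concordant |
| IN | better | yes | discordant, better |
| BN | better | yes | discordant, better |
| BI | better | no | concordant |

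The rule counts 4 of 6 moves: 2 of the 3 worsening and 2 of the 3 improving.

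**Step 2, what the pooled count measures.**
- Pooled change: C = NI + NB + IN + BN.
- All worsening: W = NI + NB + IB.
- Difference: C - W = (IN + BN) - IB.

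This is an identity and needs no assumed rates. The pooled count can lie above, at or below the number who worsened. Three illustrations in 64 women, with counts chosen only to show this and NI + NB = 4 in each:

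| IB | IN + BN | C | W | C - W |
|---|---|---|---|---|
| 2 | 5 | 9 (14.1%) | 6 (9.4%) | +3 |
| 4 | 1 | 5 (7.8%) | 8 (12.5%) | -3 |
| 2 | 2 | 6 (9.4%) | 6 (9.4%) | 0 |

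In the last row the totals agree, but only 4 of the 6 flagged women worsened.

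**Step 3, how many IB moves could there be?** The documents do not say. Assumption: 10 to 30% start intermediate and 10 to 30% of those move to BV.
- Low: 64 x 0.10 x 0.10 = 0.64 women (0.16 per arm of 16).
- High: 64 x 0.30 x 0.30 = 5.76 women (1.44 per arm of 16).

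Assume also that 10 to 30% start with BV, that 10 to 30% of intermediate women move to normal, and that 0 to 10% of BV women do. The expected C - W is 64 x [i x (to normal - to BV) + b x (BV to normal)], where i and b are the baseline shares:
- Minimum: 64 x 0.30 x (0.10 - 0.30) = -3.84.
- Maximum: 64 x [0.30 x (0.30 - 0.10) + 0.30 x 0.10] = +5.76.

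**Step 4, do other planned readouts recover the IB move?**
- *McNemar, Section 9.6.3.* It separates the two directions across the normal boundary. IB and BI do not enter it.
- *Three-category comparison, Section 9.6.3.* A net rise in BV would show. Individual moves, and IB and BI moves that cancel, would not.
- *Adverse events, Section 8.3.* Symptomatic BV can be recorded; asymptomatic BV is not.
- *Culture and qPCR, Sections 9.3.2 and 9.6.3.* These overlap biologically, but they do not count Nugent category moves.

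**The case against.** The strongest reply is that the rule is coherent. It uses the same cut as the McNemar test, a two-way definition of change suits a neutral pre/post objective, and nothing in the plan says that the count measures deterioration. All of that stands. Choosing one boundary is a legitimate preference, and the case here is that a more informative report costs almost nothing.

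It also stands that every magnitude above is assumed. The +5.76 extreme needs 60% of women to start with abnormal flora (30% intermediate plus 30% BV), which no section supports. The asymptomatic BV exception applies equally to normal-to-BV moves. The difference is that the rule and the McNemar test both catch those.

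A reader might infer three stronger things, and the documents support none of them:
- *That the plan cannot detect worsening.* The McNemar test sets worsening against improvement across the normal boundary within each arm. Only moves between intermediate and BV escape it.
- *That Fisher's test is wrongly applied to paired data.* The sentence is ambiguous. It is contrasted with a within-arm test, and the next paragraph has the parallel wording "Prevalence of microorganisms at each visit will be compared between the study arms using" Fisher's exact tests, so a between-arm reading is natural.
- *That a visit is missing.* Visit 5 is a slip. The same subsection goes on to name Visits 3 and 4, and the schedule ends at Visit 4.

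**Conclusion.** The point holds as a minor improvement to an exploratory endpoint. The rule captures 4 of 6 category moves and pools both directions, Table 7 does not restore direction, and no planned Nugent readout counts women who move from intermediate to BV. That follows from the text alone.

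The number of women affected cannot be derived from the documents. The range of 0.6 to 5.8 in 64 rests entirely on the assumed baseline and transition rates. The endpoint is not powered, and the Grade 2 or higher adverse event analysis and the sample size of 64 do not depend on it.

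**What to change.** In Section 9.3.2, define worsening as any upward category shift (normal to intermediate, normal to BV, intermediate to BV) and improvement as any downward shift. Report the two separately, each with an exact 95% interval. Show the 3x3 table of baseline (Visit 2) by follow-up category, by arm, once for Visit 3 and once for Visit 4. Align the Nugent row of Table 7. Keep the planned McNemar test.

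A McNemar test of BV against not-BV could be added descriptively. It would have little power in an arm of 16: with all discordant pairs in one direction, 5 give an exact two-sided p of 2 x 0.5^5 = 0.0625 and 6 give 2 x 0.5^6 = 0.031.

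In the same edit, replace Visit 5 with Visits 3 and 4, and state in Section 9.6.3 that Fisher's exact test on the Nugent categories compares arms.

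The cost is SAP wording and one small table per arm and visit. The Gram stains are already scheduled, so no samples, visits or participants are added.
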